**PROTOCOL TITLE:****ENGAGED2: ExperieNces with MammoGrAphy screeninG and brEast Density 2****1.0 Study Summary**

Study Title	ENGAGED2: ExperieNces with MammoGrAphy screeninG and brEast Density 2
Study Design	Randomized Control Trial
Primary Objective	

• Phase 1: Refine interventional materials for web-based use.

• Phase 2: Test the efficacy of web-based decision support intervention for women at increased risk of breast cancer to consider uptake of MRI and chemoprevention

Secondary Objective(s)	N/A
Research Intervention(s)/ Investigational Agent(s)	Website
IND/IDE #	N/A
Study Population	Patients
Sample Size	1300
Study Duration for individual participants	Phase 1: 2 hours Phase 2: 12 months
Study Specific Abbreviations/ Definitions	

PROTOCOL TITLE:

ENGAGED2: ExperiEnces with MammoGrAphy screeninG and brEast Density 2

## 2.0 Objectives\*

### 2.1 Specific Aims.

- Specific Aim 1: Assess intervention effects on uptake and distress
- Specific Aim 2: Identify mediators/moderators of intervention impact on uptake.
- Specific Aim 3: Use trial data in an established CISNET model to extend the time horizon of the trial to estimate the lifetime costs, benefits, and harms of the intervention from different perspectives.

### 2.2 Hypotheses/Research questions.

- 1a: Compared to UC, women in the PW arm will have higher rates of MRI and chemoprevention uptake at 12-months post-randomization.
- 1b: The intervention will not lead to increased distress compared with UC.
- 1c: Women in the PW arm will have higher rates of follow-up with providers to discuss MRI/chemoprevention.
- 1d: Women in the PW arm will have higher rates of mammography maintenance.
- 2a: Consistent with PMT, higher uptake of risk management in the PW arm will be mediated by increased perceptions of cancer threat (greater awareness of personal risk, higher perceived breast cancer risk, severity and worry) and stronger coping appraisals (higher response efficacy, lower response cost for preventive services; higher self-efficacy).

## 3.0 Background\*

Over 232,000 women developed breast cancer in 2014. Many of these women were unaware of disease risk factors, their personal risk, and available risk management strategies. Along with better-known risk factors such as family history, having dense breasts is one of the strongest breast cancer risk factors. Extremely dense breast tissue affects about 10% of women, with an additional third having heterogeneously dense breasts. Women in these categories have 3-6x the risk of breast cancer as compared to women with the least density. Although breast density is measured on routine screening mammograms, it has not typically been communicated to patients. However, almost half of US states now *require* disclosure of density status following routine screening mammography and federal legislation is pending. Given these mandates, expert groups are contending with how best to inform patients about their risk.

PROTOCOL TITLE:

ENGAGED2: ExperiNces with MammoGrAphy screeninG and brEast Density 2

Guidelines have long recommended risk counseling for women with clinically elevated breast cancer risk, including discussion of chemoprevention and additional breast imaging. While chemoprevention use is an individual, preference-based decision, population use is low and efforts to improve uptake are limited. Three studies have provided decision support for chemoprevention and assessed subsequent uptake, but did not increase use. These studies did not incorporate density, which may be salient for chemoprevention since early, significant reduction in density with tamoxifen use is a marker for greater breast cancer risk reduction. Women could find this more tangible given the ability to measure changes. Beyond chemoprevention, recent guidelines recommend annual screening MRI + mammography for women with a lifetime breast cancer risk  $\geq 20\%$ . Our data suggest low MRI uptake among high risk women. In the present trial, we propose the first study to evaluate a novel approach for density disclosure. We seek to fill the clinical vacuum presented by density disclosure mandates and encourage uptake of risk management without increasing distress.

#### 4.0 Study Endpoints\*

- 4.1 *Primary Endpoint:* 12 month interview and appointment and pharmacy data for endpoints of chemoprevention, screening and physician appointments.
- 4.2 *Secondary Endpoints:* 12 month cancer-related distress, mammography maintenance, healthcare utilization
- 4.3 *Safety Endpoints:* Safety endpoints have not been established as this is a minimal risk study.

#### 5.0 Study Intervention/Investigational Agent

##### 5.1 *Phase 1: Refine interventional materials for web-based use*

[figure not shown]
**Focus Group:** For the initial phase of translation, we propose to conduct one 2-hour patient focus groups, with 8-12 women participating. The purpose of the focus group is to get input from a panel of patients to inform website development.

**Beta Testing:** After the focus group has been completed, this feedback will be used to develop a functional beta version of the website. We will recruit 20 eligible women to test the intervention procedures, including providing feedback on navigating the intervention website. Beta testing intervention procedures include: 1. Baseline phone interview, 2. Intervention website navigation, and 3. Semi-structured feedback interview and survey after 2 weeks of beta testing.

##### 5.2 *Phase 2: Randomized Control Trial*

PROTOCOL TITLE:

ENGAGED2: ExperiEnces with MammoGrAphy screeninG and brEast Density 2

Potentially eligible patients will be identified, recruited, and enrolled following a negative screening mammogram and review of a routine risk factor questionnaire administered at the time of the mammogram.

At the conclusion of consent, a baseline survey (T1) will be administered. At the conclusion of the baseline interview, participants will be randomized in equal numbers to personalized web site (PW) or usual care (UC; ACS website) via computer-generated random numbers.

Participants will be notified after randomization that they will receive instructions in approximately two weeks for them to log into the website. Women will receive login information that will take them to UC or PW. Participants will be contacted for follow-up interviews at 6-weeks (T2) and 12-months (T3).

**Control (UC) Arm:** Participants randomized to UC will receive a login that will allow them to access the UC portal and the American Cancer Society website. Our creation of a login portal to a public site will allow us to track who viewed the website, but will not allow for complete utilization data. Participants will be told that this website covers many topics that are pertinent to their health. While the participants will be able to examine any part of the website, they will be asked to review the following sections: Medicines to Reduce Breast Cancer Risk, Breast Cancer Early Detection, and the Prevention Checklist for Women. Therefore, UC participants will have the opportunity to receive much of the same general information as PW participants.

**Intervention (PW) Arm:** To enter the intervention, participants will be provided with a URL and user name with a temporary password (changed to a private password on sign-in). The first time a user signs in, she will see a welcome video with instructions and will be directed to complete the intervention in order, though she will be able to navigate at-will. Participants will see an always-present indicator that clearly shows progress. Returning participants will be provided a record and links to return. They will be able to use the intervention as often as they want. However, because we are aware many participants will not return multiple times, it will be designed to communicate key content quickly and to be effective with a single usage. Similar interventions we have designed took ~40 minutes to complete. Didactic

**PROTOCOL TITLE:****ENGAGED2: ExperiEnces with MammoGrAphy screeninG and brEast Density 2**

information in text, image, animation, and video formats will be incorporated throughout. Interactive elements will be incorporated throughout (quizzes, opportunities to enter open-ended comments, controllable animation, expansion of content for detailed topics) and most pages will include audio narration of the content. Content and interface will be written and designed to be accessible by individuals with limited computer literacy. A limited set of obvious navigation elements will ensure participants do not need to “learn” how to use the website. Clear written instructions will walk users through a linear trajectory, with more experienced users having access to menus for quicker and/or non-linear usage. Content will be large and cleanly laid out, with use of obvious titles, short sentences, and lists to allow for quick digestion of key information.

Intervention translation will be guided by PMT and International Patient Decision Aid Standards (IPDAS). IPDAS guidelines suggest that the intervention should provide: 1) factual information about the condition (breast cancer risk, risk management), including severity and likelihood of possible harms; 2) options for risk management; 3) explanation of risks/benefits of each option, 4) clarification of individual preferences about options (value clarification), and 5) guidance in using information to reach decisions. With the exception of values clarification, all components were included in our print intervention; all will be in our PW arm.

## **6.0 Procedures Involved**

### **6.1 Study design**

The grant to fund this research is awarded to Georgetown, with [name] as the Principal Investigator (PI), with Kaiser Permanente Washington being the recruitment site. [name] will have ultimate responsibility for all aspects of this study. This is a decision support intervention for women at increased risk for breast cancer due to breast density and other risk factors to consider MRI and/or chemoprevention to manage their breast cancer risk. We will test the efficacy of this web intervention vs. usual care, comparing uptake of MRI and chemoprevention. All patients will be recruited at Kaiser Permanente Washington in Seattle. Phase I will consist of conducting focus groups and beta and usability testing of intervention procedures. Phase II will conduct the randomized control trial to evaluate the efficacy of web-based breast cancer risk communication vs. usual care.

### **6.2 Procedures**

#### **Phase I: Formative Data Collection**

**1. Focus Group:** For the initial phase of translation, we propose to conduct one 2-hour patient focus groups, with 8 – 12 women participating. The purpose of the focus group is to get input from a panel of patients to inform website development. Women for the focus group will be recruited from Kaiser Permanente Washington in Seattle, WA. The Kaiser Permanente Washington programmer will identify patients using Kaiser Permanente Washington administrative data, who are age 40 – 69, receive care in the greater Seattle area and have had a negative screening mammogram as part of their routine care within the past 6 months. From this pool

PROTOCOL TITLE:

ENGAGED2: ExperiEnces with MammoGrAphy screeninG and brEast Density 2

we will select a sample for outreach, oversampling to include diversity in race, ethnicity, and education level.

Participants will attend an evening focus group which will last approximately 2 hours. The focus groups will be moderated by an experienced facilitator ([name]) using a semi-structured guide. The group will be audio-recorded and a court reporter will be present to transcribe the discussion in real-time. The local Group Health Research Institute Investigator will also attend the focus group discussions. At least one assistant, and possibly two will attend the group to aid the Facilitator, completing informed consent, manage the audio recorder, manage refreshments, and distribution of remuneration. The Facilitator will answer any questions and the Facilitator or one of the assistants will complete an informed written consent with each participant before beginning the discussion. Participants will also be asked to complete a brief demographic questionnaire (attached). The study will provide receive free parking or transport and light refreshments (sandwiches, salads, cookies) for focus group participants. The Facilitator will give each participant \$50 renumeration at the end of the group as a thank you for participating.

**2. Usability testing:** This Phase will consist of 10 women to visually demonstrate usability testing and initial response to content of the final beta version of the website. The Kaiser programmer will identify patients with Kaiser Permanente Washington administrative data using the following criteria: females aged 40-69 who have received a routine mammogram and are at-risk for breast cancer. Breast cancer risk will be assessed using a risk factor questionnaire provided routinely in mammography visits. This scantron-based patient risk factor questionnaire is part of Kaiser's obligation as a member in the Breast Cancer Surveillance Consortium (BCSC). Based on this questionnaire, women with high 5-year ( $>1.66\%$ ) risk for breast cancer, and high breast density (heterogeneously or extremely dense), will be eligible for recruitment.

From this pool, we will select a sample for outreach, oversampling to include diversity in race, ethnicity, and education level. Kaiser study staff will mail potential participants a letter that invites them to participate in the study. The letter will give a telephone number to call if the woman wants to participate or does not want to be contacted further. Kaiser study staff will follow-up with a telephone call to individuals who have not actively declined to confirm interest and eligibility and give more information about the study. The study staff will mail a confirmation letter to participants who are confirmed, along with a copy of the consent form to review prior to attending usability testing session. With the participant's permission, study staff will also send a letter to her Kaiser primary care provider to alert them to the participant's risk status and let them know that she may be following up.

Usability testing will take place at Kaiser offices in Seattle WA and will last approximately 2 hours. Participants will complete a brief demographic survey before usability testing. During testing, participants will be asked to navigate

PROTOCOL TITLE:

ENGAGED2: ExperiencEs with MammoGrAphy screeninG and brEast Density 2

through a draft version of the website very much as a typical participant, but not tailored to their specific breast cancer risk, from the point of login forward. Participants will be asked to “think aloud” as they navigate the website, sharing their thought process as they work, so that Kaiser staff can gain better insight into the navigation process. They will be asked to note any feature or content that confuses them or leads to specific questions. Staff will respond in open-ended neutral ways (“What do you mean by that? Tell me more about that.”) so as not to lead the participant. If problems are identified, potential solutions or adaptations will be discussed with the participant. Usability guide is attached. Staff also will observe body language and facial expressions as additional sources of information. The goal of these sessions is to ensure that the website is functioning properly and that navigation elements are properly aligned for the participants’ experience. Participants will receive \$50 for their time. All in-person meetings will be audio recorded and reviewed to inform finalized intervention development for Phase II. We will complete testing and make changes to the intervention.

**3. Beta Testing:** After the focus group has been completed, this feedback will be used to develop a functional beta version of the website.

We will recruit 20 eligible women to test the intervention procedures, including providing feedback on navigating the intervention website. Women will be recruited from the Kaiser Permanente Washington in Seattle, WA, using the same means as the usability testing.

Kaiser study staff will mail eligible patients a letter inviting them to participate in the beta testing of intervention procedures. Beta testing intervention procedures include: 1. Baseline phone interview, 2. Intervention website navigation, and 3. Semi-structured feedback interview and survey after 2 weeks of beta testing. The invitation letter will provide a telephone number for Group Health to call if participants would like to first ask questions about the study, call to consent and schedule their participation, and/or who do not want to be contacted further. The baseline phone interview will last about 30 minutes.

Participants will be notified at the end of the baseline interview that they will receive a letter and if requested email with information in order for them to log into the intervention site. With the participant’s permission, study staff will also send a letter to her Kaiser primary care provider to alert them to the participant’s risk status and let them know that she may be following up. Before sending the letter/email to the participant, Kaiser study team staff members will organize the following data to be sent via secure data transfer for People Designs to tailor the intervention: 1. Participant study ID number, 2. Assigned username and temporary password, 3. BCSC 5 and 10 year risk estimates. The intervention will be designed to monitor utilization through website metrics (e.g., page views, feature utilization, time on site, repeat logins). All of these data points will be aggregated by People Designs and sent securely back to Kaiser to update tracking in Kaiser’s database system and for future trial analytics. After a two-week beta testing period,

PROTOCOL TITLE:

ENGAGED2: ExperiEnces with MammoGrAphy screeninG and brEast Density 2

participants will complete a follow-up interview and provide feedback to evaluate the relevance, acceptability, credibility, and comprehensibility of the information and interface. We will gather their feedback with a semi-structured phone interview to inform the intervention site. Feedback interviews will last about 30 minutes and be scheduled at participants' convenience with Kaiser staff. Participants will receive \$20 for completion of the first interview, and \$30 for the second interview, up to \$50 total for their participation.

**4. RCT Trial:** Kaiser will recruit women as they receive a negative screening mammogram. Patients routinely complete a scantron patient risk factor questionnaire at the time of the mammogram as part of Kaiser's membership in the BCSC. A Kaiser study programmer who works with the BCSC will use these risk factor data and density readings to identify eligible patients. Women will have either (a) an intermediate 5-year risk ( $>1.67\%-2.49\%$ ) and extremely dense breasts or (b) a high 5-year risk ( $\geq 2.50\%$ ) and either heterogeneously dense or extremely dense breasts. Women must also have a valid email address. Patients will be recruited via an introductory letter from the study team. This letter will notify them of their density status and introduce them to the study. Kaiser Survey Research Program will use standardized methodology for proactive telephone contact, verbal consent and to conduct baseline interviews. At the conclusion of the baseline interview, participants will be randomized in equal numbers to personalized web site (PW) or usual care (UC; ACS website) via computer-generated random numbers. Participants will be notified at the end of the call that they will receive a letter from Group Health in approximately two weeks in order for them to log into the website. During this time, personalized risk information will be sent to People Designs via secure data transfer to tailor the intervention. Women will receive login information that will take them to UC or PW. Logins will be tracked and follow-up will be made as needed to prompt uptake. Consent will be done online after website login. Patients will have the option to print a copy of the consent for them to keep. For participants that don't login to the website and give consent, they will be sent a paper consent form to sign and return. Patients that don't complete consent will not be contacted for the 12 month follow up survey and will be purged from the database. Patients will have several ways to make appointments at Kaiser and their primary care provider will be notified of their participation. We will conduct follow-up interviews at 6 weeks and 12 months. We chose 6 weeks to gather data as close in time to baseline and their initial mammogram as possible, but allow for women to receive their login and view materials. Use of Kaiser Survey Research Program ensures internal validity of data collection, diminishes missing data and allows seamless integration of survey data with clinical and pharmacy records that will serve as our primary outcome measures and inputs to our cost model. Women will receive a \$20 gift card for each interview.

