## **22.0 Consent Process**

*22.1* Participants will complete an informed written consent prior to the beginning of the focus group at Group Health in Seattle. [name] and [name] will co-lead the group and will obtain consent. The facilitator ([name]) will address all participants at the beginning of the focus group and explain study procedures and benefits/risks. Women will have a few minutes to independently read and sign the consent form prior to the start of the focus group discussions. To allow time for them to fully consider their participation, they will be mailed a copy of the consent in advance so that they can review before attending. This will also minimize undue influence, as they can choose to not attend the group or to call study staff if they have questions prior to attending.

Usability testing: Participants will complete an informed written consent and HIPAA prior to the beginning of testing at Kaiser in Seattle. To allow

PROTOCOL TITLE:

ENGAGED2: ExperiEnces with MammoGrAphy screeninG and brEast Density 2

time for them to fully consider their participation, they will be mailed a copy of the consent in advance so that they can review before the interview.

Beta testing: Participants will complete consent and HIPAA online thru the intervention website. They will receive the same consent language as in a written consent but in an online format and will be required to agree to the consent and check yes to move forward into the tailored information of the website.

Usability testing: Participants will complete an informed written consent and HIPAA prior to the beginning of testing at Kaiser in Seattle. To allow time for them to fully consider their participation, they will be mailed a copy of the consent in advance so that they can review before the interview.

RCT: Participants will complete consent and HIPAA upon logging into the study website for the first time. We have requested an alteration of consent to allow consent to be completed online. Participants will have the option to print a copy of the consent to keep. For participants that never log into the study website a paper consent will be mailed to them to sign and return.

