***Non-English Speaking Subjects***

- n/a

***Waiver or Alteration of Consent Process (consent will not be obtained, required information will not be disclosed, or the research involves deception)***

- We are requesting a limited HIPAA waiver to support recruitment. All information obtained for individuals who are not retained as participants will be destroyed.
- We are opting for an online consent as the primary means of consent for anyone using the website (PW or UC) as we have concerns with potential participants accessing and using the intervention website in advance of returning signed written consent and possibly without ever returning the signed written consent. We want to be sure there is clear communication regarding the elements of consent and have documentation of consent before participants enter into the tailored information of the website. Written paper consent will be used as a back-up for those who do not log on. Those who do not return this paper consent will not be contacted for the 12 month and will be purged from the dataset.

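### Randomized women who complete neither online nor paper consent are purged, so the primary analysis is not intention-to-treat as Section 17.1 states

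*Combined protocol and SAP*

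**What the plan says.** The order of events is set out in Section 6.2 (item 4, RCT Trial) and Section 5.2.

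- The survey group carries out "proactive telephone contact, verbal consent and to conduct baseline interviews".
- Allocation follows at once: "At the conclusion of the baseline interview, participants will be randomized in equal numbers".
- About two weeks later, "Women will receive login information that will take them to UC or PW".
- Section 22.0 places the governing consent at that point: "Participants will complete consent and HIPAA upon logging into the study website for the first time". A paper form is mailed to women who never log in.
- The consequence of completing neither is stated twice. Section 6.2 has "Patients that don't complete consent will not be contacted for the 12 month follow up survey and will be purged from the database". Section 22.0, under waiver or alteration of consent, has "Those who do not return this paper consent will not be contacted for the 12 month and will be purged from the dataset". The same part adds "All information obtained for individuals who are not retained as participants will be destroyed".

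Section 17.1 says that every analysis is intention-to-treat. Because the primary outcomes are administrative, it keeps all women who consented and completed the baseline (N=1250). It deducts 5% health-plan attrition to reach 1188 (594 per arm), and divides by a design effect of 1.2 to reach an effective 990. The survey outcomes have an effective 842. Section 17.1 does not mention the purge.

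**The concern.** The purge acts on women who already have an allocation. A set built that way is not ITT, whatever its label. Section 17.1 justifies full retention by the administrative outcomes, which need no survey response; the purge defeats that reasoning. Section 14.0 makes the contrast sharper: a woman who withdraws keeps her existing data in the analysis unless she objects, while a woman who merely fails to complete a form is deleted.

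Three things are at stake. The MRI and chemoprevention comparisons would be reported under a label that they do not meet. The primary set depends on which consent is meant, and the analysis section does not say. Once records are destroyed, the ITT set cannot be rebuilt, and the multiple imputation in Section 17.1 cannot recover women who are no longer in the data.

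**Working it through.** **1. The plan's own figures.** 1250 × 0.95 = 1187.5, stated as 1188. Design effect 1 + (11 − 1) × 0.02 = 1.20, and 1188/1.2 = 990. The chain reproduces. The whole step from 1250 to 1188 is health-plan attrition, so nothing in it allows for purging.

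**2. The two readings of *consented* in Section 17.1.**

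- *Online or paper consent.* The 1250 are what remains after the purge. The 1188, 990 and 842 stand, but the set is selected after randomization.
- *Verbal consent.* The 1250 are the women randomized. The purge then deletes women whom Section 17.1 promises to keep, and 1188 and 990 hold only if nobody is purged.

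Neither reading gives an ITT analysis once anyone is purged.

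**3. Possible bias.** The documents give no purge rate. The usual-care uptake rates are in Table 5, which is not in the supplied text. All rates here are therefore assumptions: no true effect, uptake p = 5% in both arms, and 594/1.2 = 495 effective women per arm before purging. With purge fraction q and uptake u among purged women:

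- observed rate in an arm: r = (p − q·u)/(1 − q)
- remaining effective size: n = 495 × (1 − q)
- d = r₁ − r₂, with SE₀ the pooled and SE₁ the unpooled standard error
- type I error = Φ((−1.96·SE₀ − d)/SE₁) + 1 − Φ((1.96·SE₀ − d)/SE₁)

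Example, 10% v 30% purged, u = 2.5%: r₁ = (0.05 − 0.0025)/0.90 = 5.28%; r₂ = (0.05 − 0.0075)/0.70 = 6.07%; n = 445.5 and 346.5; d = −0.79 points; type I error 7.9%.

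| Uptake among purged women | 10% v 20% purged | 10% v 30% purged |
|---|---|---|
| Average (5%) | 5.0% | 5.0% |
| Half (2.5%) | 5.6% | 7.9% |
| Zero | 7.2% | 15% |
| Double (10%) | 7.9% | 21% |

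Zero uptake is not the worst case. Below-average uptake among purged women flatters the more heavily purged arm; above-average uptake does the reverse. Equal purging keeps 5% only if purged women's uptake is the same in both arms: 10% purged in each, with uptake 0% v 10% among them, gives about 12%.

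**4. Power, only if 1250 is the number randomized.** Effective n per arm = 1250 × (1 − q) × 0.95/1.2/2. Take an effect with 80% power at 495 per arm, for example 5% v 9.63%.

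- q = 10%: 1069 women, 891 effective, power 75.7%.
- q = 20%: 950 women, 792 effective, power 70.7%.

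If the design effect falls as clusters shrink, these become 76.5% and 72.3%.

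**5. Room within 1300, only if 1250 is the number after the purge.** 1300 − 1250 = 50 women. Phase 1 uses 38 to 42 (8–12 focus group, 10 usability, 20 beta). If 1300 includes them, 8 to 12 are left. If purged women do not count as participants, 1300 sets no limit.

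**The case against.** The best defence is that Section 22.0 calls online consent the primary means of consent in both arms. On that reading Section 17.1 and the purge agree, and no sample-size figure is wrong. This largely stands. The ambiguity is real but not even-handed, and the general documentation paragraph in Section 23.0, which covers verbal and online consent alike, is weak support for the other reading. It does not rescue the ITT label.

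The plan also has features that limit a difference between arms. Online consent comes before any tailored content, both arms have the paper route, and "Logins will be tracked and follow-up will be made as needed to prompt uptake". These make a large imbalance less likely. They do not rule it out, because the login leads to the assigned arm and no blinding of the prompting is described.

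Section 14.0 promises to track withdrawals, and Section 17.1 to assess attrition. Neither commits to purge counts by arm.

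Three stronger readings are tempting and are not supported:

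- That women are randomized without consent. Verbal consent comes first.
- That the comparison is biased. No document gives a purge rate, a difference between arms, or a link with uptake.
- That the survey outcomes lose power. The purge bars only the 12-month contact, so these women may already fall within the stated 10% loss at 12 months.

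**Conclusion.** The point holds. A rule stated in two sections removes women after randomization, and this contradicts the ITT statement in Section 17.1 on either reading of *consented*. That conclusion rests on the text and needs no assumed rate.

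The consequences are conditional. Bias requires purge rates, or uptake among purged women, that differ by arm; unequal purge rates do no harm if purged women have average uptake. The type I error range of 5.6% to 21% belongs to the assumed differentials of 10 and 20 percentage points, which no passage suggests are likely. The loss of power to about 76% or 71% applies only if 1250 is the number randomized.

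It must be fixed because it concerns the primary analysis set and because destruction of records cannot be undone.

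**What to change.** Amend the protocol before any record is purged:

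1. State in Section 17.1 which consent defines the primary set, and reconcile it with Sections 6.2 and 22.0.
2. Replace ITT with modified ITT: randomized women with completed online or paper consent by a stated deadline, the same in both arms.
3. Keep and report non-identifying counts by arm of women randomized, logged in, consented and purged.
4. Add a sensitivity analysis that assigns purged women uptake from zero to above the observed rate (for example twice it), varied separately by arm. It needs only the purged counts.
5. If 1250 is the number randomized, restate N and power with a purge allowance.

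The cost is text and aggregate counts, a less favourable label, and possibly less favourable N and power. Any bias is made visible, not removed.

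A stronger option, if still feasible, is to randomize only after the governing consent. It needs a neutral portal, later allocation and more baseline interviews: 1250/0.9 = 1389 or 1250/0.8 = 1563 to randomize 1250 at an assumed 10% or 20% non-completion. Keeping administrative outcomes for every randomized woman would restore ITT, but depends on approval beyond the limited recruitment waiver now requested.
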